Duration of response (DOR) is defined as the time from first response to confirmed loss, progression of disease, or on-treatment death due to any cause ([date of loss – date of first response]/7). Response is unconfirmed for cytogenetic and molecular and confirmed for hematologic with 2 consecutive responses at least 28 days apart. Confirmed loss is defined as 2 consecutive non-responses at least 28 days apart for MCyR and 14 days apart for hematologic, 1 non-response confirmed by progression of disease or death, or no loss of response and progression of disease or death. For CCyR, confirmed loss is defined as 2 consecutive assessments with >0 Ph⁺ metaphases or $\geq 1\%$ positive cells from fluorescence in situ hybridization (FISH) at least 28 days apart or progression or death. For MMR, confirmed loss is defined as 2 consecutive assessments at least 28 days apart with a <3 -log ($>0.1\%$ from B1871006 or MR² or worse denoted on the B187040 case report form [CRF]) reduction in transcripts from standardized baseline one of which corresponds to a ≤ 2 -log reduction ($\geq 1\%$ from B1871006 or MR¹ or worse denoted on the B1871040 CRF) or progression or death. For MR⁴, confirmed loss is defined as 2 consecutive assessments at least 28 days apart with a <4 -log ($>0.01\%$ from B1871006 or MR³ or worse denoted on the B187040 CRF) reduction in transcripts from standardized baseline one of which corresponds to a ≤ 3 -log reduction ($\geq 0.1\%$ from B1871006 or MR² or worse denoted on the B1871040 CRF) or progression or death. Patients without confirmed loss are censored at the last valid assessment where response could be assessed. Cytogenetic and hematologic responses are defined in [Appendix 2](#) and [Appendix 1](#). MCyR is defined as a CCyR or partial cytogenetic response (PCyR). OHR is defined as CHR or return to chronic phase (RCP). To be considered a responder, the patient must have an improvement from baseline or maintenance of baseline response for ≥ 5 weeks for hematologic response or ≥ 4 weeks for cytogenetic response. Patients with a non-valid cytogenetic assessment (<20 metaphases) or missing baseline assessment must demonstrate the best response, CCyR or CHR, to be considered a responder for the respective endpoint.

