8.2.1. Analysis of Efficacy Endpoints

The duration of cytogenetic, hematologic, and molecular response analyses are based on the full analysis set for the subset of B1871006 patients who respond for the respective endpoint. The K-M method, as described in [Section 8.1](#), will be used provided most responding patients transferred to B1871040 remain on treatment until progression or loss of response. The percentage of MR⁴, MMR, MCyR, CCyR, and PCyR and CHR and major hematologic response (MHR)/OHR (advanced patients only) for the respective endpoint, along with confirmed losses and censored patients still on-treatment will be summarized.

The time to transformation analysis is based on the full analysis set for the B1871006 patients. Cumulative incidence of transformation adjusting for the competing risk of treatment discontinuation due to any reason without transformation, as described in [Section 8.1](#), will be used. The percentage of transformation without treatment discontinuation and the percentage of treatment discontinuation due to any reason without transformation will be summarized. The specific disease stage transformation (accelerated or blast phases) will also be listed.

The PFS analysis is based on the full analysis set for the B1871006 patients. The K-M method, with or without unsatisfactory response as assessed by the investigator as an event and cumulative incidence of on-treatment progression or death adjusting for the competing risk of treatment discontinuation due to any reason without the event, as described in [Section 8.1](#), will be used. For K-M, the percentage of on-treatment death or progression, with or without unsatisfactory response as an event, will be summarized. For cumulative incidence, the percentage of on-treatment death or progression without treatment discontinuation and the percentage of treatment discontinuation due to any reason without on-treatment progression and death will be summarized.

The OS analysis is based on the full analysis set for all patients. The K-M method, as described in [Section 8.1](#), will be used. The number of deaths and causes of death will be summarized. Time on study from date of randomization for B1871008 patients and date of first dose for B1871006 patients to date of last contact, and reasons for discontinuing participation will also be summarized.

The percentage of patients with emergent mutations will be summarized.

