Appendix 1. HEMATOLOGIC RESPONSE DEFINITIONS

Hematologic Responses	Definition

Return to Chronic Phase (RCP) (or CP for subjects with CP) Minor Hematologic Response (MiHR) (for Ph+ ALL subjects) Subjects had to meet all criteria
	
Disappearance of features defining accelerated and blast phases, but still in chronic phase as noted by:
 
 • <15% Blasts in both blood and marrow • <30% Blasts + promyelocytes in both blood and marrow • <20% Basophils in both blood and marrow (marrow not applicable for Ph+ ALL) • No extramedullary involvement other than liver/spleen

Accelerated Phase had to meet at least 1 criterion
	
 • 15-29% Blasts in blood or marrow • ≥30% Blasts + promyelocytes in blood or marrow • ≥20% Basophils in blood or marrow 
only applicable to advanced phase
 
 • Platelets <100x10⁹/L (not related to therapy)

Blast Phase had to meet at least 1 criterion
	
 • ≥30% blasts in blood or bone marrow • Extramedullary involvement other than liver/spleen

No Evidence of Leukemia (NEL) had to meet all criteria
	
 • WBC ≤ institutional ULN • 450 x10⁹/L > Platelets ≥20x10⁹/L • ANC ≥0.5x10⁹/L • <20% basophils in blood • No blasts or promyelocytes in blood • Myelocytes + metamyelocytes <5% in blood • No extramedullary involvement (incl. hepato- or splenomegaly) 
only applicable for advanced phase
 
 • ≤5% bone marrow blasts

Complete Hematologic Response (CHR) had to meet all criteria
	
 • WBC ≤ institutional ULN • Platelets <450 × 10⁹/L • <20% basophils in blood • No blasts or promyelocytes in blood • Myelocytes + metamyelocytes <5% in blood • No extramedullary involvement (incl. hepato- or splenomegaly) 
only applicable to advanced phase
 
 • ≤5% bone marrow blasts • ANC ≥1.0 × 10⁹/L • Platelets ≥100 × 10⁹/L

Overall Hematologic Response (OHR) had to meet at least 1 criterion
	
CHR +NEL +RCP + MiHR (if applicable)

Major Hematologic Response (MHR) (had to meet at least 1 criterion)
	
CHR +NEL

Abbreviations: ANC=absolute neutrophil count, ULN=upper limit of normal range, WBC=white blood cell count

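### SAP 6.1 and Appendix 1 define overall hematologic response differently, so OHR rates and durations in advanced patients can depend on which definition is programmed

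*SAP*

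**What the plan says.** - SAP 6.1 lists duration of OHR as an endpoint for the advanced B1871006 patients. Its text then says "OHR is defined as CHR or return to chronic phase (RCP". NEL and MiHR are not named.
- Just before that, the same paragraph says "Cytogenetic and hematologic responses are defined in" Appendix 2 and Appendix 1.
- SAP Appendix 1 gives OHR as at least one of "CHR +NEL +RCP + MiHR (if applicable". Protocol Appendix 1 has the same entry. Both appendices define major hematologic response (MHR) as CHR or NEL.
- MiHR has no row of its own. It appears in the RCP row, as "Minor Hematologic Response (MiHR) (for Ph+ ALL subjects".
- SAP 8.2.1 plans percentages for "CHR and major hematologic response (MHR)/OHR (advanced patients only", together with confirmed losses.
- SAP 2.1 counts accelerated phase (AP), blast phase (BP) and Ph+ ALL patients as advanced.
- Protocol 2.2 ties the later-line efficacy endpoints to its Appendix 1.

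**The concern.** One listed endpoint has two definitions within the SAP, and the one in the body text also differs from the protocol. Neither document says which governs, or whether the hematologic levels are cumulative (a patient can hold several at once) or exclusive (each visit receives one best category). Two programmers could follow the SAP correctly and report different OHR responders, rates and durations.

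Duration is the more exposed of the two. For hematologic response, SAP 6.1 counts two successive non-responses at least 14 days apart as confirmed loss. If NEL is not part of OHR, a patient moving from CHR to NEL could be recorded as having lost overall response. So could a patient who improves from RCP to NEL.

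**Working it through.** The plan has no design figure to reproduce here. The check sets the Appendix 1 criteria for advanced patients side by side and asks which NEL patients the phrase CHR or RCP misses.

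| Criterion | CHR | NEL | RCP bullets |
|---|---|---|---|
| WBC | at most ULN | at most ULN | none |
| Platelets (x 10^9/L) | 100 to <450 | 20 to <450 | none |
| ANC (x 10^9/L) | ≥1.0 | ≥0.5 | none |
| Blasts, promyelocytes in blood | none allowed | none allowed | blasts <15%, sum <30% |
| Basophils in blood | <20% | <20% | <20% |
| Myelocytes + metamyelocytes in blood | <5% | <5% | none |
| Marrow blasts | ≤5% | ≤5% | <15% |
| Marrow blasts + promyelocytes | no limit on the sum | no limit on the sum | <30% |
| Marrow basophils | no limit | no limit | <20% (not for Ph+ ALL) |
| Extramedullary disease | none | none | none beyond liver/spleen |

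**Step 1: which NEL states are at issue.** Every CHR state also meets NEL. The states that are NEL but not CHR have ANC 0.5 to <1.0, or platelets 20 to <100, or both.

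**Step 2: NEL against the RCP bullets.** NEL satisfies "<15% Blasts in both blood and marrow" and the blood and extramedullary limits. It leaves open the marrow parts of "<30% Blasts + promyelocytes in both blood and marrow" and "<20% Basophils in both blood and marrow (marrow not applicable for Ph+ ALL". An NEL patient therefore fails the RCP bullets only if marrow blasts plus promyelocytes reach 30% (with blasts at most 5%, promyelocytes of at least 30 − 5 = 25%), or marrow basophils reach 20%.

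**Step 3: the RCP header.** The header asks that accelerated-phase and blast-phase features be gone. For advanced patients, platelets below 100 not caused by therapy are an accelerated-phase feature. If the header is a criterion in its own right, an NEL patient with such platelets (20 to <100) is not RCP. If only the bullets count, this gap does not exist.

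**Step 4: the two coding conventions under the SAP 6.1 wording.**

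| | Exclusive categories | Cumulative levels |
|---|---|---|
| NEL-only visits | all outside OHR | outside only in the gaps of steps 2 and 3 |
| Confirmed CHR-to-NEL change | loss of OHR | loss only in those gaps |
| MHR nested in OHR | not guaranteed | yes, apart from those gaps |

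**Step 5: MiHR.** It uses the RCP row, with the marrow basophil limit waived for Ph+ ALL. Omitting the name changes results only if code selects on the label.

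**Step 6: size.** Protocol 1.2.2 reports confirmed OHR by Week 48 of 55.1% in AP (n=69) and 28.3% in BP (n=60). Implied counts are 0.551 × 69 ≈ 38 and 0.283 × 60 ≈ 17. One patient is worth 1/69 = 1.4 points or 1/60 = 1.7 points. The number k of patients counted under only one definition is not in the documents, so the k values below are assumptions. Intervals are exact 95%.

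| k removed | AP | BP |
|---|---|---|
| 0 | 38/69 = 55.1% (42.6 to 67.1) | 17/60 = 28.3% (17.5 to 41.4) |
| 1 | 37/69 = 53.6% (41.2 to 65.7) | 16/60 = 26.7% (16.1 to 39.7) |
| 3 | 35/69 = 50.7% (38.4 to 63.0) | 14/60 = 23.3% (13.4 to 36.0) |
| 5 | 33/69 = 47.8% (35.6 to 60.2) | 12/60 = 20.0% (10.8 to 32.3) |

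These denominators are the parent study's evaluable patients. SAP 8.2.1 bases duration of response on responders in the full analysis set, so the table shows scale only.

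**The case against.** The best defence is that SAP 6.1 sends the reader to Appendix 1 just before the OHR sentence. That sentence can then be taken as shorthand, and a programmer who follows the reference reaches the protocol's definition. Read by its bullets and cumulatively, RCP already takes in nearly all NEL patients, and MiHR is RCP under another name. The platelet gap depends on treating a header as a criterion and applies only to low platelets not caused by therapy. It also reflects an ambiguity in Appendix 1 itself, where one patient could meet both NEL and accelerated phase. Finally, the study tests no hypothesis and names no primary endpoint.

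Much of this stands, and it limits the effect. It does not remove the conflict. The sentence is worded as a definition, not a summary, and nothing gives the appendix precedence. Nothing states that levels are cumulative either, and the RCP row's description of patients as still in chronic phase can be read as a level distinct from NEL. SAP Section 1 records no deliberate narrowing of OHR. It does say that version 2.0 updated the appendix criteria, which fits a body sentence left unaligned, though that is inference.

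A reader might go further and infer that the results must differ, that Ph+ ALL responders are lost, or that OHR would no longer be comparable with the parent-study rates. The documents support none of these. The first needs exclusive coding or patients in the narrow gaps. The second needs code that selects on the label. The third cannot be checked, because Protocol 1.2.2 does not say which OHR definition produced its rates.

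**Conclusion.** The inconsistency is real and unresolved: OHR rates and durations in advanced patients can differ according to the definition programmed. The effect is broad only under exclusive coding, which neither document specifies. Under cumulative coding it is confined to the marrow gaps and, if the RCP header is enforced, the platelet gap. The number of patients affected is unknown and may be zero. The per-patient shift of 1.4 points (AP) or 1.7 points (BP) is an illustration, not an estimate. Severity is minor to moderate: it concerns a listed but descriptive endpoint in the advanced cohorts.

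**What to change.** In SAP 6.1:

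1. Replace the OHR sentence with the Appendix 1 definition: CHR, NEL, RCP, or MiHR for Ph+ ALL.
2. State whether the levels are cumulative or exclusive.
3. State that movement among these categories is not loss of OHR.

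With the first change, OHR includes every NEL patient under either coding convention, apart from the possible overlap of NEL with the accelerated-phase platelet feature, and MHR is nested in OHR. The second change is still needed for that overlap and for any reporting of single categories. The cost is two or three sentences and a programming check before database lock. No new data are needed.

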5.3. Bosutinib Treatment Discontinuation

Patients meeting any of the following criteria should discontinue bosutinib:

1. Disease progression, including:
 - Evolution from chronic phase (or from return to chronic phase for advanced patients) to accelerated phase or blast crisis (on two consecutive assessments at least a week apart).
 - Evolution from accelerated phase to blast crisis (on two consecutive assessments at least a week apart).
 - One of the following conditions occurring after dose escalation (as specified in [Section 5.2.1](#), Dose Escalation) or presence of adverse events prohibiting dose escalation:
 - For 1st line patients, loss of complete or major cytogenetic response (need at least 30% increase confirmed by a follow-up cytogenetic analysis >1 month later). Cytogenetic assessment done as part of standard of care practice will be used to determine the cytogenetic response status.
 - For 2nd or later line patients, loss of major cytogenetic response (need at least 30% increase).
 - For all lines of treatment, loss of complete hematologic response confirmed by 2 assessments at least 2 weeks apart.
 - For all lines of treatment, increasing WBC defined as doubling of WBC, occurring over a period of ≥ 1 month, with the second WBC $>20 \times 10^9/L$ and confirmed at least 1 week later.
2. Bosutinib treatment interruption for longer than 4 weeks due to treatment-related toxicity, unless decided (and documented) otherwise by the investigator and Sponsor (see [Table 3](#) and [Table 4](#)).
3. Bosutinib dose reduction below 300 mg/day. Except if after documented discussion with the investigator and Sponsor, it has been determined as appropriate for the patient to continue on bosutinib dose below 300 mg/day. No dose reductions below 200 mg/day will be permitted.
4. Withdrawal of consent.
5. Sponsor decision.
6. Pregnancy.

7. Death.

Survival follow-up information will be obtained for all patients who discontinue bosutinib treatment. See Treatment Completion and Follow-up section for detailed procedures to be performed upon treatment completion and for LTFU.

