9.5. Progression-Free Survival

Progression-free survival (PFS) is the interval from the date of first dose of bosutinib in the parent study until the earlier date of progression or death from any cause. Patients without events are censored at the last evaluation date.

PFS will be calculated only for patients in 2nd or above line setting.

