Molecular response in B1871006 was based on the difference between the subject's change in Bcr-Abl/Abl ratio and a laboratory reference baseline. The Quest (vendor) laboratory reference Bcr-Abl/Abl ratio of 4.1325 derived from a pool of 120 previously untreated CML subjects was used as the standardized (or reference) baseline. Molecular response was not analyzed for subjects in China, India, the Russian Federation, and South Africa due to logistical constraints in transporting samples to the central laboratory.

To be considered a responder for MMR in B1871006, a subject must have had at least a 3-log reduction from the Quest standardized baseline, a detectable Bcr-Abl transcript at baseline or any time post-baseline, and must have maintained or attained a CCyR. Additionally, as a conservative approach given the known variability with standard MMR analyses, a subject who had a non-CCyR on the same day as the MMR assessment was not considered to have a MMR at that time point. MR⁴ was defined similar to MMR except at least a 4-log reduction was required. In B1871040, responders had MMR/MR⁴ or better denoted on the CRF as assessed by a local laboratory. On-treatment response is independent of a patient's baseline molecular response.

PFS is defined as the time from first dose to progression as assessed by the investigator and noted as the reason for permanent treatment discontinuation on the CRF or on-treatment death due to any cause ($[\text{date of progression/death} - \text{first dose date}]/30.4$), whichever occurs first. Patients without events are censored at the last cytogenetic, hematologic, or laboratory assessment where progression could be assessed. Progression for B1871006 patients is defined as:

- *Evolution from chronic phase (or from return to chronic phase for advanced subjects) to accelerated phase or blast crisis (on two consecutive assessments at least a week apart).*
- *Evolution from accelerated phase to blast crisis (on two consecutive assessments at least a week apart).*
- *One of the following conditions occurring after dose escalation or presence of adverse events prohibiting dose escalation:*
 - *For 2nd or later line subjects, loss of major cytogenetic response (need at least 30% increase).*
 - *For all lines of treatment, loss of complete hematologic response confirmed by 2 assessments at least 2 weeks apart.*

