 - *For all lines of treatment, increasing WBC defined as doubling of WBC, occurring over a period of ≥ 1 month, with the second WBC $> 20 \times 10^9/L$ and confirmed at least 1 week later.*

For DOR and PFS, if there is an unacceptable gap between the date of progression or death and the date of the most recent prior disease assessment (>48 weeks), the event will not be used and censorship will be at the most recent prior assessment.

Transformation, defined by the first two progression bullets above, is the time from first dose to confirmed transformation ($[\text{date of transformation} - \text{first dose date} + 1]/7$). Confirmed transformation is defined as 2 consecutive assessments at least 1 week apart or 1 assessment confirmed by progression of disease or death. Patients without events are censored at the last hematologic or extramedullary assessment where transformation could be assessed.

BCR-ABL mutational status at treatment discontinuation will be assessed. Emergent mutations are defined as those mutations which were not present at baseline. B1871006 patients who were not assessed for baseline mutations are not assessable for emergent mutations. All B1871008 patients are assessable for emergent mutations.

OS is defined as the time from randomization for B1871008 patients and from first dose B1871006 patients to the date of death ($[\text{date of death} - \text{randomization/first dose date}]/30.4$). Patients who have not died will be censored at the last known alive date.

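### PFS counts progression only when it is the CRF reason for stopping bosutinib, so a confirmed transformation to AP/BP can be a transformation event without being a PFS event

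*SAP*

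**What the plan says.** **PFS event, SAP 6.1.** The event is "progression as assessed by the investigator and noted as the reason for permanent treatment discontinuation on the CRF", or death from any cause while on treatment, whichever comes first. For everyone else: "Patients without events are censored at the last cytogenetic, hematologic, or laboratory assessment where progression could be assessed".

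**Progression criteria, SAP 6.1.** The list that follows opens with evolution from chronic phase "to accelerated phase or blast crisis (on two consecutive assessments at least a week apart"), then evolution from accelerated phase to blast crisis.

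**Transformation, SAP 6.1.** The endpoint reuses those two criteria: "Transformation, defined by the first two progression bullets above, is the time from first dose to confirmed transformation". On confirmation: "Confirmed transformation is defined as 2 consecutive assessments at least 1 week apart or 1 assessment confirmed by progression of disease or death". The recorded reason for stopping plays no part when two assessments agree.

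**PFS analyses, SAP 8.2.1.** There are two Kaplan-Meier versions, with and without investigator-assessed unsatisfactory response as an event. There is also a cumulative-incidence version, in which stopping treatment without the event is the competing risk.

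**Protocol 9.5.** PFS runs "until the earlier date of progression or death from any cause", with no condition on why treatment stopped. Protocol 5.3 lists the same two evolutions under disease progression as grounds for discontinuing, for example "Evolution from accelerated phase to blast crisis (on two consecutive assessments at least a week apart").

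**The concern.** The SAP treats confirmed evolution to AP/BP as progression, derives a date for it, and then does not use that date for PFS. Whether it becomes a PFS event depends on what the site enters as the reason for stopping. The study report could show the same patient as transformed and as having no progression event.

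The resulting censoring is informative. It removes the patient from the risk set because of failure, at or near the time of failure, so Kaplan-Meier PFS is too high. A later death need not correct this. Only on-treatment death counts for PFS, and SAP section 6 ends the on-treatment efficacy period for B1871006 patients at treatment discontinuation. A death in long-term follow-up therefore enters overall survival but not PFS.

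**Working it through.** The plan has no sample size, test or event target that depends on this definition, so there is no figure to reproduce. The check applies the SAP's rules to one type of patient and then looks at direction and scale.

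**1. The rules applied.** Take a chronic-phase B1871006 patient with two consecutive AP- or BP-range assessments at least one week apart.

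| What happens next | Transformation | K-M PFS | K-M PFS with unsatisfactory response | Cumulative-incidence PFS |
|---|---|---|---|---|
| Stops, CRF reason is progression | Event | Event | Event | Event |
| Stops, CRF reason is an adverse event or withdrawn consent | Event | Censored | Censored | Competing event |
| Stops, CRF reason is unsatisfactory response | Event | Censored | Event | Competing event |
| Stays on bosutinib | Event | No event at that date; stays at risk | Same | Same |

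The censoring date in rows 2 and 3 is the last assessment at which progression could be judged, which may be the one that showed AP/BP. In row 4 a PFS event arises only if progression is later recorded as the reason for stopping, or the patient dies on treatment; it is delayed or missed. In no version does the confirmed transformation itself count as a PFS event.

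**2. Direction.** Toy example with 10 patients: PFS events at months 6 and 18, one confirmed transformation at month 12 with another reason for stopping, and no other loss before month 18.

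- Transformation censored: (9/10) × (7/8) = 0.7875.
- Transformation counted: (9/10) × (8/9) × (7/8) = 0.700.

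The current rule gives the higher figure.

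**3. Scale.** Protocol 1.2.2 gives n = 288 second-line chronic-phase patients and a two-year PFS of 80.6%. Let m be the number of discordant patients by two years; m is not in the documents. With no other censoring, counting them as events lowers PFS by at most about m/n. The second column assumes an effective n of 200 to allow for other censoring.

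| m (assumed) | 80.6% − m/288 | 80.6% − m/200 |
|---|---|---|
| 1 | 80.3% | 80.1% |
| 5 | 78.9% | 78.1% |
| 10 | 77.1% | 75.6% |

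For comparison, a simple binomial 95% half-width at 80.6% is 1.96 × √(0.806 × 0.194 / 288) = 4.6 percentage points. The documents do not say that the 80.6% was obtained under the present rule, so it serves only as a scale.

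**The case against.** **Sites would normally record progression.** Protocol 5.3 puts evolution to AP/BP first among the progression grounds for stopping, and the SAP repeats those criteria. Consistent recording would make discordant patients uncommon, and the documents show none. This stands as a limit on size. But neither document requires the recorded reason to agree with the derived transformation.

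**Investigator-assessed PFS is a legitimate choice.** So it is. But the SAP also lists objective criteria as the definition of progression and does not say which governs when they disagree with the CRF. Two programmers could derive different PFS dates.

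**Nothing is hidden.** Transformation is a separate endpoint on the same full analysis set, the stage reached is listed, all efficacy data are listed, and one Kaplan-Meier version adds unsatisfactory response. That helps a careful reader, but it does not correct any PFS estimate except where unsatisfactory response was the recorded reason.

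**Derived transformation can misfire.** In advanced patients the accelerated-phase platelet criterion excludes therapy-related falls, which needs judgement, and SAP section 7 takes the lowest of several platelet values. This is true, but it applies equally to the transformation endpoint as planned.

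**Stronger readings that a reader might infer.** None of these is supported:

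- *A patient kept on drug is censored at transformation or counted as a competing discontinuation.* That patient has not stopped and remains at risk.
- *Duration of response has the same defect.* Its definition in SAP 6.1 carries no CRF-reason condition and also counts loss derived from assessments.
- *The problem is worse in accelerated phase.* The documents give nothing on this.
- *The SAP breaches the protocol.* Protocol section 9 lets the SAP modify the plan, with major endpoint changes reflected in the study report.

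**Conclusion.** The concern holds for PFS in B1871006 patients. As written, SAP 6.1 allows a confirmed transformation that is not a PFS event, and no analysis in SAP 8.2.1 counts it as one. For patients who stop for another recorded reason, the Kaplan-Meier censoring is informative and the bias is upward. For patients kept on drug, the event is late or absent.

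The size is unknown. It depends on how many patients have a derived transformation and a different recorded reason. Under the assumptions above, 1 to 10 such patients by two years would lower an 80.6% estimate by up to about 0.3 to 3.5 percentage points with n = 288, or 0.5 to 5.0 with an effective n of 200. Protocol 5.3 points to the low end.

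The SAP has no hypotheses or decision rules (sections 4.1 and 4.2), so only descriptive estimates are affected. The change is still worth making, because the contradiction is internal to the SAP and the date needed is already derived.

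**What to change.** In SAP 6.1, define the PFS event date as the earliest of:

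- progression recorded by the investigator as the reason for discontinuation;
- the SAP's own derived confirmed on-treatment transformation to AP/BP, whatever reason for stopping is recorded;
- on-treatment death.

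If comparability with earlier reports is wanted, keep the CRF-based PFS alongside and report the definition above as a sensitivity analysis. Carry the chosen event through the Kaplan-Meier and cumulative-incidence versions in SAP 8.2.1.

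Add a listing of patients whose derived transformation and CRF discontinuation reason disagree. For duration of response, one sentence is enough: its progression component uses the same progression date.

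The cost is SAP wording, one extra condition on a date already programmed, and one listing; no new data are needed. The downside is that PFS may be slightly less favourable and differ a little from earlier reports.
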